8.5.2 Survey Data Collection

- The PI ([name]) or other IRB-approved research personnel will conduct two interviews with the patient: (1) the first interview will occur following extubation (i.e. removal of the breathing tube after CABG surgery) within a 6 – 24 hour post-surgical window; (2) the second interview will occur at any point between 1 – 5 days post-surgery. These interviews will take approximately 15 – 30 minutes.

Clinical Study Number:	NCT06154265	Document Title:	10/24/2024	Page 16 of 36
		Default vs As-Needed Intraoperative Transesophageal Echocardiography (TEE) in Low-Risk Isolated Coronary Artery Bypass Graft (CABG) Surgery: A Randomized Controlled Trial		

- No identifying information from the patient will be collected. Survey data will be labeled only by subject number.
- Patient Interview Questions
 - 1. Did you, or do you currently have symptoms of throat soreness?
 - 2. Does your throat feel dry or scratchy?
 - 3. Have you had difficulty swallowing liquids, pills, or food?
 - 4. Has swallowing been painful?
 - 5. Have you felt nauseous or vomited?
 - 6. Have you had symptoms of acid reflux?
 - 7. Did you ever have the taste of blood in your mouth?
 - 8. Have you had any GI symptoms I haven't asked you about?

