5.1 Detailed Product Description of Equipment

Figure 1: Transesophageal Echocardiography Probe

Figure 1: This image is a photograph of a Philips transesophageal echocardiography (TEE), ultrasound probe. During cardiac surgeries, this probe is passed through the

Clinical Study Number:	NCT06154265	Document Title:	10/24/2024	Page 10 of 36
		Default vs As-Needed Intraoperative Transesophageal Echocardiography (TEE) in Low-Risk Isolated Coronary Artery Bypass Graft (CABG) Surgery: A Randomized Controlled Trial		

patients oropharynx and advanced into the esophagus and/or stomach to acquire real-time, ultrasound-based, cardiac images during surgery.
<https://www.usa.philips.com/healthcare/resources/feature-detail/ultrasound-tee-imaging>

Clinical Study Number:	NCT06154265	Document Title:	10/24/2024	Page 11 of 36
		Default vs As-Needed Intraoperative Transesophageal Echocardiography (TEE) in Low-Risk Isolated Coronary Artery Bypass Graft (CABG) Surgery: A Randomized Controlled Trial		

6 Study Objectives and Purpose

The overall objective of this RCT is feasibility testing. To accomplish this, we will randomize eligible isolated CABG surgery patients to receive either default (i.e., obligatory) vs as-needed (i.e. backup) intraoperative TEE. Enrolled subjects will be randomized after induction of anesthesia. Trial outcomes will include subject recruitment, overall rate of TEE performed in the as-needed trial arm, and clinical outcomes.

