6.2 Secondary Objective(s)

- Describe the incidence of gastroesophageal symptoms, injury, or complications: defined as the rate of patient-reported gastroesophageal symptoms (e.g. painful or difficulty swallowing, hoarseness, or eating), swallowing dysfunction (defined by the need for a postoperative swallowing evaluation after surgery), or diagnosis of a new gastroesophageal problem (defined by the need for an upper endoscopy after surgery).

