- f. Initiation of phenylephrine infusion at a dose ≥ 1.5 mcg/kg/min (i.e. exceeding 100 mcg/min) for a duration \geq minutes
- g. Initiation of vasopressin infusion at a dose ≥ 0.04 units/min for a duration ≥ 5 minutes

7 Withdrawal of Subjects

Study participation is voluntary. Subjects may refuse to consent or withdraw from the study at any time without penalty or loss of benefits.

8 Overview of RCT

This study will be a prospective, parallel design, randomized controlled trial.

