8.3 Randomization and Trial Protocol

8.4.1 Randomization

- Randomization will occur on the day of surgery after placement of an arterial line for invasive hemodynamic monitoring (routine for all patients undergoing isolated CABG surgery) and following induction of anesthesia and successful placement of the endotracheal tube. This will ensure that any patient who is hemodynamically unstable (defined by the exclusion criteria listed above) following induction of anesthesia is excluded from the trial (and will receive an obligatory intraoperative TEE).

Clinical Study Number:	NCT06154265	Document Title:	10/24/2024	Page 15 of 36
		Default vs As-Needed Intraoperative Transesophageal Echocardiography (TEE) in Low-Risk Isolated Coronary Artery Bypass Graft (CABG) Surgery: A Randomized Controlled Trial		

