11.1 Risks Associated with Trial Participation

- The following risks are inherent to participation in this RCT:
 - (1) Risk of gastroesophageal harm from the TEE probe itself: Patients in the default TEE treatment arm will be exposed to, (patients in the as-needed TEE treatment arm may be exposed to) the gastroesophageal clinical risks associated TEE. Patients in the as-needed TEE treatment arm may be exposed to the gastroesophageal clinical risks associated with the use of The current cardiac surgery literature indicates that the risk of clinically significant gastroesophageal injury ranges 0.1% – 4%.¹⁷⁻²⁰ On balance, patients randomized to the default TEE trial arm will have a greater risk of gastroesophageal injury than patients randomized to the as-needed TEE trial arm.
 - (2) Risk of harm from the absence of continuous TEE monitoring during isolated CABG surgery: Patients randomized to the as-needed intraoperative TEE arm may be exposed to potential negative consequences associated with delayed diagnoses of hemodynamic instability. For instance, if EKG changes are detected intraoperatively and a TEE is deemed necessary (by the cardiac surgeon or cardiac anesthesiologist) to investigate for potential regional wall motion abnormalities caused by graft ischemia, confirmation of the diagnosis by TEE may take minutes in the as-needed TEE treatment arm (vs. seconds in the default TEE treatment arm). On balance, patients randomized to the as-needed trial arm will have greater risk of delayed diagnosis than patients randomized to the default TEE trial arm.
 - (3) Loss of time: Participating in the trial will require patients to spend additional time above and beyond the typical perioperative timeframe for undergoing an isolated CABG surgery to review trial-related information, consider the risks associated with participation in the trial (i.e. informed consent process), and answer trial-related questionnaires after surgery.
 - (4) Loss of privacy and confidentiality: Although the risk of occurrence is unlikely, there is a risk of inadvertent disclosure of protected health information (PHI),

Clinical Study Number:	NCT06154265	Document Title:	10/24/2024	Page 19 of 36
		Default vs As-Needed Intraoperative Transesophageal Echocardiography (TEE) in Low-Risk Isolated Coronary Artery Bypass Graft (CABG) Surgery: A Randomized Controlled Trial		

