- (4) Study-Related AE or SAE – An AE or SAE is considered study-related if the principal investigator (PI) determines that the AE or SAE is definitely, probably, or possibly related (where possibly related is defined as a reasonable probability that the AE or SAE may have been caused by randomization to default or as-needed intraoperative TEE). Any AE or SAE deemed to be remotely related or not related to randomization is not considered to be study-related.
- (5) Unanticipated Problem or Unexpected AE or SAE – Problems or events in which trial participation places patients or others at a greater risk of harm (including physical, psychological, economic, or social) than was previously known or recognized. The term “unanticipated problem” is used in this context because some situations may not have produced an adverse event but may still be considered an unanticipated problem (e.g. an incidence of unsecured patient data which may not result in a breach of confidentiality). An event is unexpected if it is not described in the study protocol or informed consent document.
- (6) Each AE that is tracked will be assessed for:
- a. Grade:
 - i. Grade 1 Mild; asymptomatic or mild symptoms; clinical or diagnostic observations only; intervention not indicated.
 - ii. Grade 2 Moderate; minimal, local or noninvasive intervention indicated; limiting age-appropriate instrumental Activities of Daily Living (ADL)
 - iii. Grade 3 Severe or medically significant but not immediately life-threatening; hospitalization or prolongation of hospitalization indicated; disabling; limiting self-care or ADLs.
 - iv. Grade 4 Life-threatening consequences; urgent intervention indicated
 - v. Grade 5 Death related to AE.
 - b. Relatedness to trial participation:
 - i. Definitely
 - ii. Probably
 - iii. Possibly
 - iv. Remotely
 - v. Unrelated
 - c. Expectedness after cardiac surgery
 - i. Expected
 - ii. unexpected
 - d. Severity
 - i. Mild
 - ii. Moderate
 - iii. severe

Clinical Study Number:	NCT06154265	Document Title:	10/24/2024	Page 29 of 36
		Default vs As-Needed Intraoperative Transesophageal Echocardiography (TEE) in Low-Risk Isolated Coronary Artery Bypass Graft (CABG) Surgery: A Randomized Controlled Trial		

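### No masking of patients or interviewers is specified for the symptom interviews, although randomization under anesthesia makes it practicable at low cost

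*Combined protocol and SAP*

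**What the plan says.** **Design and allocation.** Section 8 describes the design in one sentence: "This study will be a prospective, parallel design, randomized controlled trial". It attaches no term for masking. Section 6 says "Enrolled subjects will be randomized after induction of anesthesia", and Section 8.4.1 places randomization after the arterial line and "following induction of anesthesia and successful placement of the endotracheal tube".

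**Collection.** Under Section 8.5.2 the PI or "other IRB-approved research personnel will conduct two interviews with the patient". The first interview follows extubation, 6 to 24 hours after surgery; the second falls on days 1 to 5. Eight questions are listed, covering such matters as sore or dry throat, swallowing, nausea and reflux, with an open catch-all at the end. The nearest thing to concealment is "Survey data will be labeled only by subject number", which protects confidentiality and does not mask anyone.

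**Use.** Section 6.2 has the gastroesophageal outcome "defined as the rate of patient-reported gastroesophageal symptoms", or a swallowing evaluation, or an upper endoscopy. Section 10.2 lists it first among the secondary endpoints and says that clinical data are collected with a future trial in mind. Section 19.5.1 plans Chi-squared and Wilcoxon tests by intention to treat.

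**Expectation.** Section 19.2.1 has staff present current data on the risks and benefits of TEE at recruitment. Section 11.1 states that "patients randomized to the default TEE trial arm will have a greater risk of gastroesophageal injury than patients randomized to the as-needed TEE trial arm".

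**The concern.** Whether a throat feels sore or swallowing has been painful depends on what the patient expects and on how the question is put. If both parties know the arm, and both have been told that TEE may injure the throat or esophagus, the natural drift is toward more reported symptoms under default TEE. That is also the direction the protocol anticipates, so a reporting artifact would look like confirmation.

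The composite definition adds to this. Its components are joined by *or*, so a single reported symptom can make a patient positive with no objective finding.

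At stake is the credibility of the symptom comparison as an input to planning the next trial. A small sample widens the interval around a difference, whereas differential reporting moves the difference itself, and a larger trial run the same way would not remove it.

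**Working it through.** No figure in the plan bears on this point, and Section 19.5.2 says no formal power calculation was done, so there is nothing to reproduce. The check has two parts.

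**1. Who could know the arm?**

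- *Patient.* Unconscious at allocation (Sections 6 and 8.4.1). Nothing says whether the patient is told the arm before the interviews.
- *Research staff.* Section 8.5.1 has the PI or other approved personnel collect the medical-record data, and Section 8.5.2 draws interviewers from the same group.
- *PI.* Permitted as interviewer by Section 8.5.2. Section 19.1.1.4 gives the PI daily safety monitoring and weekly data audits, including of the medical record. Section 19.1.1.1 has the PI judge whether an event "may have been caused by randomization to default or as-needed intraoperative TEE", which in practice requires knowing the arm.

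Following the protocol exactly as written therefore allows an interviewer who knows the arm.

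**2. How large could the effect be?**

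Inputs from the documents: 22 per arm (Section 10.3), or 22 in total (Section 19.5.2), which is 11 per arm if allocation is 1:1. Assumptions, because the documents give no values: true symptom rate p equal in both arms (40%, range 20% to 60%), and extra reporting d in the default arm.

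SE of the difference = sqrt(2p(1 − p)/n).

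- p = 0.40 (or 0.60), n = 22: sqrt(0.48/22) = 0.148
- p = 0.40 (or 0.60), n = 11: sqrt(0.48/11) = 0.209
- p = 0.20, n = 22: sqrt(0.32/22) = 0.121
- p = 0.20, n = 11: sqrt(0.32/11) = 0.171

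At p = 0.40, a shift of 10 to 15 points is 10/14.8 to 15/14.8 = 0.7 to 1.0 SE with 22 per arm, and 10/20.9 to 15/20.9 = 0.5 to 0.7 SE with 11 per arm. At p = 0.20 the ranges are 0.8 to 1.2 and 0.6 to 0.9.

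The chance of a falsely significant result was found by exact enumeration. For x and y positives in two arms of n, with s = x + y, chi-squared = (x − y)² · 2n / [s(2n − s)]. The product of the binomial probabilities at p + d and p is summed wherever this exceeds 3.841 (two-sided 5%, no continuity correction; the plan states neither alpha nor sidedness). Results over p = 20%, 40% and 60%:

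| Extra reporting d | 22 per arm | 11 per arm |
|---|---|---|
| 0 | 4.7–5.1% | 3.4–4.9% |
| 10 points | 10–12% | 7–8% |
| 20 points | 26–30% | 16% |
| 30 points | 52–67% | 30–34% |

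For comparison, the 95% half-width for the difference at p = 0.40 is 1.96 × 14.8 = 29 points, or 1.96 × 20.9 = 41 points. A moderate reporting shift would usually lie inside the noise, yet would still displace the estimate.

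**The case against.** The strongest reply is that the protocol is silent, and silence is not unmasked conduct. A reader might infer that the interviews are open-label. The documents do not say so: neither that term nor *blinded* appears, and nothing says that patients learn their arm or that interviewers know it. The consent form and the part on study team roles (Section 19.3.1), where such arrangements might appear, were not available to me. This stands. The defect is that masking is unspecified, and bias *can* enter; it is not shown that it does.

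A reader might also infer that masking costs nothing. It does not quite: the PI may have to give up interviewing, someone unaware of the arm must be free in each window, and clinicians or the patient portal may reveal the arm. Patient masking also presumes that the probe is out before waking, which is plausible from its intraoperative use but not stated.

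Nor are these symptoms specific to TEE. Every patient is intubated, and sore throat or nausea can follow in either arm. That makes them common rather than harmless, because differential reporting still shifts the difference.

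Finally, the consequence is limited. Neither primary endpoint depends on the interviews, and Sections 10.2 and 19.5.2 disclaim power for clinical outcomes. A reader might go further and put a number on a misdirected future sample size. The documents do not support that: they say clinical data will help with planning, but not that a symptom difference will set the next sample size. What survives is that the arms are nevertheless to be compared by test, on data whose collection leaves this route to bias open.

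**Conclusion.** The point holds as a gap in specification with a low-cost remedy. As written, the protocol permits arm-aware interviewing for a subjective secondary outcome, in patients told of the risk beforehand, although allocation under anesthesia makes patient masking practicable.

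The size is illustrative. It rests on an assumed 40% symptom rate and an assumed 10 to 15 point reporting shift, neither of which has a source in the documents. It also depends on which sample size is meant, and Sections 10.3 and 19.5.2 need to be reconciled. On those assumptions the shift is about 0.7 to 1.0 SE at 22 per arm, or 0.5 to 0.7 SE at 11 per arm.

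Masking patients and interviewers would protect only the reported symptoms. Swallow evaluations and endoscopies can be ordered by clinicians who know the arm. The feasibility conclusions on recruitment and on TEE use in the as-needed arm stand regardless.

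**What to change.** Amend Sections 8.4 and 8.5.2 to say:

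1. Patients are not told their arm until interview 2 is complete, unless disclosure is clinically needed or the patient asks.
2. Interviews are done by an existing team member who was not in that operating room and has not opened the intraoperative record; not by the PI if the PI knows the arm.
3. The questions already listed are asked as a fixed script.
4. At the end of interview 2, after the symptom questions, the patient's guess of arm is recorded. It should be reported descriptively, since patients with symptoms may guess TEE for that reason.
5. Reported symptoms are presented separately from swallow testing and endoscopy.

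The consent form should say that the arm will be withheld until interview 2. Adverse-event reporting to the PI is unchanged.

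Cost: a consent-form sentence, one added question and a scheduling constraint. Whether present staffing can meet that constraint cannot be confirmed from the available text, although Section 8.5.2 already permits interviewers other than the PI. Some unmasking through clinicians or the patient portal will remain; the recorded guess gives some indication of how much, which is useful to know before a multicenter trial.

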19.2 Recruitment and Retention Plan

19.2.1 Recruitment Plan

- Recruitment for the randomized controlled trial (RCT) will occur through the Penn Presbyterian Medical Center (PPMC) cardiac surgery clinic of the University of Pennsylvania Health System. Within our Institutional Review Board (IRB) protocol, we will request permission to access clinic and surgical schedules of potential isolated coronary artery bypass graft (CABG) patients in order to identify potential RCT subjects that meet inclusion and exclusion criteria for enrollment in the trial. Once a potential subject has been identified, he or she will be approached in-person, pre-procedure. After a brief introduction, either the research assistant (RA) or the principal investigator (PI) will approach these patient participants and ask if they would be interested in hearing about the trial. If they agree, the RA or PI will ask a series of additional screening questions to confirm that the patient meets eligibility criteria. If the patient is deemed eligible and expresses interest in learning more about the study, the RA or PI will review the intent of the study, present the current data regarding risks and benefits to using intraoperative transesophageal echocardiography (TEE) during isolated CABG surgery. Once the patient agrees to participate, the RA or PI will complete the enrollment process by providing an information packet, collecting basic demographic and health data, reviewing study timeline and protocols, and obtaining written informed consent that confirms the study subjects' agreement to participate in the RCT as specified in the trial protocol and the subjects' permission to allow the research team to access electronic medical records. Patients will receive an incentive for completing all phases of the study. The trial inclusion and exclusion criteria for subject participation listed in the above-protocol will be confirmed and finalized with [name] prior to initiation of recruitment.

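### The postoperative symptom interviews cannot separate new from long-standing symptoms, so pre-existing swallowing difficulty, and possibly reflux, can be counted in the secondary gastroesophageal incidence

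*Combined protocol and SAP*

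**What the plan says.** Section 6.2 (Secondary Objectives) sets out to describe an incidence with three components: patient-reported symptoms, with painful or difficult swallowing, hoarseness and eating as examples; need for a postoperative swallowing evaluation; and "diagnosis of a new gastroesophageal problem", shown by the need for upper endoscopy. Newness is required only in the third. Section 10.2 lets reported symptoms alone meet the outcome. It asks for clinical significance, without defining it, and limits the outcome to the hospital stay.

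Section 8.5.2 (Survey Data Collection) plans two interviews, both after surgery: "the first interview will occur following extubation", within 6–24 hours, and "the second interview will occur at any point between 1 – 5 days post-surgery". The items include "Have you had difficulty swallowing liquids, pills, or food", "Have you had symptoms of acid reflux", "Did you ever have the taste of blood in your mouth" and "Did you, or do you currently have symptoms of throat soreness".

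Preoperative information comes from the medical record (8.5.1), from medical and surgical history (15.1) and from the enrollment visit, which includes "collecting basic demographic and health data" (19.2.1). None of these sections mentions swallowing, throat or reflux symptoms. The exclusions in 6.3.2 cover several esophageal, gastric and oropharyngeal conditions, but neither reflux disease nor dysphagia as such. Section 19.5.1 plans Chi-squared and Wilcoxon rank-sum tests by intention to treat, and a description of presurgical comorbidities by arm.

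**The concern.** An incidence counts events that begin during the period at risk, here after randomization and possible probe placement. A patient who has had trouble swallowing for years can truthfully answer yes to the swallowing item after surgery. Nothing in the plan distinguishes that answer from one given by a patient whose difficulty began after the operation.

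Randomization balances earlier symptoms between arms on average. It does not remove them from the rate within each arm, which is what 6.2 sets out to describe, and it does not prevent dilution of the difference. In arms this small a chance imbalance is also likely. Section 10.2 says the clinical data are collected to help plan a later, powered trial, so inflated rates and a diluted difference could be carried into that planning.

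**Working it through.** The documents give no expected symptom rate and no power calculation (19.5.2), so there is no planned figure to reproduce. The check has two parts.

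**1. Do the texts separate new from old symptoms?**

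- The swallowing and reflux items have no recall period. The taste-of-blood item asks about any time. The throat-soreness item covers past or present, and the throat-dryness item is in the present tense. None asks whether the symptom is new, worse, or began after surgery.
- The hospital-stay limit in 10.2 fixes when a symptom must be present, not when it started.
- No section says how the eight answers become an event. Because 6.2 names swallowing difficulty, a chronic case fits its definition. Reflux is asked about but not named in 6.2, so whether it counts is open.
- No rule uses chart history or enrollment data to remove or adjust for earlier symptoms.

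**2. What would mixing them do?**

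Let p be the true risk of a new symptom and b the proportion with a pre-existing symptom. Assume the two are independent and that everyone with a pre-existing symptom answers yes. Then:

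- measured rate = 1 − (1 − p)(1 − b)
- inflation = b(1 − p)
- measured difference = (1 − b) × true difference

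The inputs are assumptions: b of 10, 20 and 30%, and true rates of 20% and 40%. For example, at b = 10% the rates are 1 − 0.80 × 0.90 = 28% and 1 − 0.60 × 0.90 = 46%.

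| b | Measured rates | Difference | Expected patients with prior symptoms, arm of 22 |
|---|---|---|---|
| 0 | 20% vs 40% | 20 points | 0 |
| 10% | 28% vs 46% | 18 points | 2.2 |
| 20% | 36% vs 52% | 16 points | 4.4 |
| 30% | 44% vs 58% | 14 points | 6.6 |

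*Chance imbalance.* Take 22 per arm (10.3) and independent binomial counts. The probability that the arms differ by three or more patients with pre-existing symptoms is 20%, 34% and 41% at b = 10, 20 and 30%. Three patients are 3/22, or about 14 percentage points.

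*Later planning.* Suppose a trial were sized on these symptom rates, with two-sided 5% significance and 80% power (both assumed). It would need about 82 per arm at b = 0, and 112, 150 and 199 at b = 10, 20 and 30%.

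*Precision for comparison.* With true rates of 20% and 40% and 22 per arm, the 95% half-width of the difference is 1.96 × √[(0.20 × 0.80 + 0.40 × 0.60)/22] = 1.96 × √(0.40/22) = 0.264, or about 26 points.

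**The case against.** Several points on the other side stand.

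- The timing of the items is not wholly open: two refer at least partly to the present, and 10.2 confines the outcome to the hospital stay. Neither feature identifies onset.
- A reader might infer that every patient with chronic reflux will be scored as an event. The documents do not support that. There is no scoring rule, 6.2 does not name reflux, and 10.2 requires clinical significance. For reflux, one can say only that it may be counted.
- The comorbidity description in 19.5.1 could show charted reflux or dysphagia by arm, if it is captured, and so expose an imbalance. It would miss unrecorded symptoms, and no rule would take them out of the rate.
- The dilution of 2–6 points is small beside a half-width of about 26 points. This trial is not powered for clinical outcomes and says so. The dilution is systematic, however, and would persist in a larger trial using the same items.
- A reader might also apply the 0.1–4% range quoted in sections 4 and 11.1 and arrive at a far larger distortion. That range is for gastroesophageal injury, a different outcome from reported symptoms, so it cannot serve as the symptom rate here.
- Section 10.2 lists four groups of clinical outcomes for planning and does not say that the symptom rate will size the later trial. The sample sizes above are therefore illustrative.

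**Conclusion.** The point holds for the symptom component of one secondary outcome. As written, the plan calls this component an incidence but cannot separate new from pre-existing symptoms. The direction follows from the formula: rates too high in both arms, and a difference shrunk by (1 − b). The size is not known, because b appears nowhere in the documents. The fall from 20 to 18–14 points rests wholly on the assumed b of 10–30%, the assumed rates of 20% and 40%, independence, and full reporting of earlier symptoms.

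A reader might infer that the trial's main results are compromised. They are not: the two primary endpoints are recruitment and TEE use in the as-needed arm, and neither uses the interviews. The swallow-evaluation and endoscopy components do not depend on the item wording either. This is an inexpensive improvement worth making because baseline answers cannot be reliably recovered after surgery.

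**What to change.** 1. In 8.5.2, begin each postoperative item with wording such as *Since your operation, have you had new …*.
2. Ask the same items once, before surgery, at the existing consent contact, and record them on the case report form.
3. In 6.2 and 10.2, state which items count toward the outcome, including whether reflux does. Define an incident symptom as absent at baseline and present at a postoperative interview. Worsening from baseline can be used only if a simple severity grade is added at both times, because the present items have none.
4. In 19.5.1, report crude and baseline-corrected incidence by arm.

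The rewording costs nothing beyond a protocol change. The baseline questions add a few minutes and one form page for up to 75 consented patients (10.3), some of whom will never be randomized. The baseline may precede surgery by days or weeks, so a symptom starting in that gap could still be taken as new; the reworded items reduce that risk.
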